8.2.11.2. Ongoing Tuberculosis Evaluation

Early Detection of Active Tuberculosis

To aid in the early detection of TB reactivation or new TB infection during study participation, participants must be evaluated for signs and symptoms of active TB at scheduled visits (refer to the SoA in Section 1.3) or by telephone contact approximately every 8 to 12 weeks. The following series of questions is suggested for use during the evaluation:

- “Have you had a new cough of >14 days’ duration or a change in a chronic cough?”
- “Have you had any of the following symptoms:
 - Persistent fever?
 - Unintentional weight loss?
 - Night sweats?”
- “Have you had close contact with an individual with active TB?” (If there is uncertainty as to whether a contact should be considered “close,” a physician specializing in TB should be consulted.)

If the evaluation raises suspicion that a participant may have TB reactivation or new TB infection, an immediate and thorough investigation should be undertaken, including, where possible, consultation with a physician specializing in TB.

Investigators should be aware that TB reactivation in immunocompromised participants may present as disseminated disease or with extrapulmonary features. Participants with evidence of active TB should be referred for appropriate treatment.

Participants who experience close contact with an individual with active TB during the conduct of the study must have a repeat chest radiograph, a repeat QuantiFERON[®]-TB test, a repeat tuberculin skin test in countries in which the QuantiFERON[®]-TB test is not approved/registered or the tuberculin skin test is mandated by local health authorities, and, if possible, referral to a physician specializing in TB to determine the participant’s risk of developing active TB and whether treatment is warranted. Study intervention administration should be interrupted during the investigation. A positive QuantiFERON[®]-TB test or tuberculin skin test result should be considered detection of latent TB. Participants with a newly identified positive QuantiFERON-TB[®] test result must undergo an evaluation to rule out active TB and initiate appropriate treatment for latent TB. Appropriate treatment for latent TB is defined according to local country guidelines for immunocompromised patients. If no local country guidelines for immunocompromised patients exist, US guidelines should be followed, or the participant will be excluded from the study. If the QuantiFERON-TB[®] test result is indeterminate, the test should be repeated. Participants should be encouraged to return for all subsequent scheduled study visits according to the protocol. Participants who discontinue treatment for latent TB prematurely or who are noncompliant with therapy must immediately discontinue further administration of study intervention and be encouraged to return for all subsequent scheduled study visits according to the SoA (Section 1.3).

8.3. Adverse Events, Serious Adverse Events, and Other Safety Reporting

Timely, accurate, and complete reporting and analysis of safety information, including AEs, SAEs, and PQC, from clinical studies are crucial for the protection of participants, investigators, and the sponsor, and are mandated by regulatory agencies worldwide. The sponsor has established Standard Operating Procedures in conformity with regulatory requirements worldwide to ensure appropriate reporting of safety information; all clinical studies conducted by the sponsor or its affiliates will be conducted in accordance with those procedures.

Adverse events will be reported by the participant (or, when appropriate, by a caregiver, surrogate, or the participant's legally acceptable representative) for the duration of the study.

For study intervention that meets the definition of a combination product, malfunctions or deficiencies of a device constituent will be reported as PQC.

Further details on AEs, SAEs, and PQC can be found in Appendix 10 [Section 10.10], Adverse Events, Serious Adverse Events, Product Quality Complaints, and Other Safety Reporting: Definitions and Procedures for Recording, Evaluating, Follow-up, and Reporting.

8.3.1. Time Period and Frequency for Collecting Adverse Event and Serious Adverse Event Information

All Adverse Events

All AEs and special reporting situations, whether serious or non-serious, will be reported from the time a signed and dated ICF is obtained until completion of the participant's last study-related procedure, which may include contact for follow-up of safety.

Serious Adverse Events

All SAEs, as well as PQC, occurring during the study must be reported to the appropriate sponsor contact person by study-site personnel within 24 hours of their knowledge of the event.

Serious adverse events, including those spontaneously reported to the investigator by the final safety visit, must be reported using a serious adverse event form. The sponsor will evaluate any safety information that is spontaneously reported by an investigator beyond the time frame specified in the protocol.

A possible Hy's Law case is defined by the occurrence of ALT or AST $\geq 3xULN$ together with total bilirubin $\geq 2xULN$ or INR > 1.5 (if measured). Any possible Hy's Law case is considered an important medical event and should be reported to the sponsor in an expedited manner using the Serious Adverse Event form, even before all other possible causes of liver injury have been excluded.

Information regarding SAEs will be transmitted to the sponsor using the Serious Adverse Event Form, which must be completed and signed by a physician from the study site, and transmitted to the sponsor within 24 hours. The initial and follow-up reports of an SAE should be made by facsimile (fax). Telephone reporting should be the exception and the reporter should be asked to complete the appropriate form(s) first.

8.3.2. Method of Detecting Adverse Events and Serious Adverse Events

Care will be taken not to introduce bias when detecting AEs or SAEs. Open-ended and nonleading verbal questioning of the participant is the preferred method to inquire about AE occurrence.

Solicited Adverse Events

Solicited AEs are predefined local at the injection site and systemic events for which the participant is specifically questioned.

Unsolicited Adverse Events

Unsolicited AEs are all AEs for which the participant is not specifically questioned.

8.3.3. Follow-up of Adverse Events and Serious Adverse Events

The investigator is obligated to perform or arrange for the conduct of supplemental measurements and evaluations as medically indicated to elucidate the nature and causality of the adverse event, serious adverse event, or PQC as fully as possible. This may include additional laboratory tests or investigations, histopathological examinations, or consultation with other health care professionals.

Adverse events, including pregnancy, will be followed by the investigator as specified in Appendix 10 [Section 10.10], Adverse Events, Serious Adverse Events, Product Quality Complaints, and Other Safety Reporting: Definitions and Procedures for Recording, Evaluating, Follow-up, and Reporting.

8.3.4. Regulatory Reporting Requirements for Serious Adverse Events

The sponsor assumes responsibility for appropriate reporting of AEs to the regulatory authorities. The sponsor will also report to the investigator (and the head of the investigational institute where required) all SUSARs. The investigator (or sponsor where required) must report SUSARs to the appropriate IEC/IRB that approved the protocol unless otherwise required and documented by the IEC/IRB. A SUSAR will be reported to regulatory authorities unblinded. Participating investigators and IEC/IRB will receive a blinded SUSAR summary, unless otherwise specified.

8.3.5. Pregnancy

All initial reports of pregnancy in female participants or partners of male participants must be reported to the sponsor by the study-site personnel within 24 hours of their knowledge of the event using the appropriate pregnancy notification form. Abnormal pregnancy outcomes (eg, spontaneous abortion, fetal death, stillbirth, congenital anomalies, ectopic pregnancy) are considered SAEs and must be reported using an SAE reporting form. Any participant who becomes pregnant during the study must discontinue further study intervention.

Follow-up information regarding the outcome of the pregnancy and any postnatal sequelae in the infant will be required (see Appendix 5 [Section 10.5], Contraceptive and Barrier Guidance and Collection of Pregnancy Information and Appendix 10 [Section 10.10, Adverse Events, Serious Adverse Events, Product Quality Complaints, and Other Safety Reporting: Definitions and Procedures for Recording, Evaluating, Follow-Up, and Reporting]).

8.3.6. Disease-Related Events and Disease-Related Outcomes Not Qualifying as Adverse Events or Serious Adverse Events

Flares of lupus activity, including LN (defined as an increase in proteinuria and/or serum creatinine concentration, abnormal urine sediment or a reduction in creatinine clearance rate as a result of active disease requiring a change in an immunomodulatory medication for LN beyond that which is outlined in Section 6.5), that meet the definition of an SAE will be reported to the sponsor but will not be reported to the Health Authorities during the trial so that blinding may be retained in order to ensure study integrity.

8.3.7. Adverse Events of Special Interest

Any newly identified malignancy or case of active TB occurring after the first study intervention administration(s) in participants in this clinical study must be reported by the investigator to the sponsor or designee within 24 hours after being made aware of the event, according to the procedures in Appendix 10 (Section 10.10), Adverse Events, Serious Adverse Events, Product Quality Complaints, and Other Safety Reporting: Definitions and Procedures for Recording, Evaluating, Follow-Up, and Reporting, for SAEs. Investigators are also advised that active TB is considered a reportable disease in most countries. These events are to be considered serious only if they meet the definition of an SAE.

8.4. Treatment of Overdose

For this study, any dose of study intervention greater than 10% above the highest dose at a single dosing visit specified in this protocol will be considered an overdose. The sponsor does not recommend specific intervention for an overdose.

In the event of an overdose, the investigator or treating physician should:

- Contact the medical monitor immediately.
- Closely monitor the participant for AE/SAE and laboratory abnormalities.
- Document the quantity of the excess dose in the eCRF.

Decisions regarding dose interruptions or modifications will be made by the investigator in consultation with the medical monitor based on the clinical evaluation of the participant.

8.5. Pharmacokinetics

Serum samples will be used to evaluate the PK of guselkumab, as well as the immunogenicity of guselkumab (antibodies to guselkumab). Serum collected for PK may additionally be used to evaluate safety or efficacy aspects that address concerns arising during or after the study period. Genetic analyses will not be performed on these serum samples. In addition, 24-hour urine samples will be used to evaluate the potential renal excretion of guselkumab. Participant confidentiality will be maintained.

8.5.1. Evaluations

Venous blood samples of approximately 5 mL will be collected for measurement of serum concentrations of guselkumab and antibodies to guselkumab at the timepoints shown in the SoA (Section 1.3).

Urine samples will be collected for measurement of guselkumab according to the SoA (Section 1.3).

Venous blood samples will be collected and each serum sample will be divided into 3 aliquots (1 each for PK, anti-guselkumab antibodies, and a back-up). Samples collected for analyses of guselkumab serum concentration and antibody to guselkumab may additionally be used to evaluate safety or efficacy aspects that address concerns arising during or after the study period, for further characterization of immunogenicity or for the evaluation of relevant biomarkers. Genetic analyses will not be performed on these serum samples. Participant confidentiality will be maintained. Additional information about the collection, handling, and shipment of biological samples can be found in the laboratory manual.

8.5.2. Analytical Procedures

Pharmacokinetics

Serum and urine samples will be analyzed to determine concentrations of guselkumab using a validated, specific, and sensitive immunoassay method by or under the supervision of the sponsor. The sponsor, or its designee, under conditions in which the participants' identity remains blinded, will assay these samples.

8.5.3. Pharmacokinetic Parameters and Evaluations

Parameters

Based on the individual plasma concentration-time data, using the actual dose taken and the actual sampling times, PK parameters and exposure information of guselkumab will be derived using population PK modeling if data permits. Baseline covariates (eg, body weight, age, sex, CrCL, race) may be included in the model, if relevant.

Pharmacokinetic/Pharmacodynamic Evaluations

If data permit, the relationships between serum guselkumab concentration and selected efficacy or PD measures may be analyzed graphically.

8.6. Pharmacodynamics

Pharmacodynamic markers will be evaluated using blood and urine samples collected at visits as indicated in the SoA (Section 1.3). Postbaseline PD test results will not be released to the investigators by the central laboratory.

8.7. Genetics

A pharmacogenomic blood sample will be collected from participants who consent separately to this component of the study to allow for pharmacogenomic research, where local regulations permit. Participation in pharmacogenomic research is optional.

Genetic (DNA) variation may be an important contributory factor to interindividual variability in drug response and associated clinical outcomes. Genetic factors may also serve as markers for disease susceptibility and prognosis and may identify population subgroups that respond differently to an intervention.

8.8. Biomarkers

Biomarker assessments will be made to examine the biologic response to treatment and to identify biomarkers that are relevant to guselkumab treatment and/or LN, where local regulations permit. Assessments (detailed below) will include the evaluation of relevant biomarkers in serum, whole blood, and urine collected as specified in the SoA (Section 1.3), where local regulations permit.

Data collected from these samples will be used for exploratory research that will include the following objectives:

1. To understand the molecular effects of guselkumab.
2. To understand LN pathogenesis.
3. To understand why individual participants may respond differently to guselkumab.
4. To understand the impact of treatment with guselkumab on kidney or systemic inflammation.
5. To develop diagnostic tests to identify LN or SLE populations that may be responsive or non-responsive to treatment with guselkumab.

8.8.1. Serum-based Biomarkers

Blood samples for serum-based biomarker analyses will be collected from all participants, where local regulations permit. Serum will be analyzed for levels of specific proteins, autoantibodies, and other inflammation-related molecules and/or disease-associated serologies relevant to LN and SLE pathogenesis and treatment and response to guselkumab.

8.8.2. Whole Blood-based Biomarkers

Whole blood will be collected by venipuncture from participants for RNA expression analysis, where local regulations permit. Total RNA will be isolated and used for differential gene expression analyses to identify gene expression patterns that are relevant to guselkumab treatment and/or LN and SLE, and to evaluate markers that can predict clinical response. Transcriptome studies will be conducted using microarray, and/or alternative equivalent technologies, which

facilitates the simultaneous measurement of the relative abundances of multiple RNA species resulting in a transcriptome profile for each blood sample. This will enable the evaluation of changes in transcriptome profiles that may correlate with biological response relating to LN or SLE and/or the action of guselkumab.

Whole blood will also be collected and processed for PBMC isolation and cryopreserved for later analysis. Analysis may include but is not limited to flow cytometric assessment of cell populations, single cell transcriptomics, or functional assessment of cells in response to guselkumab treatment.

8.8.3. RNA Expression Research of a Subset of RNA Species

Urine will be analyzed for soluble proteins that may enable the identification of markers related to LN or SLE disease activity and markers associating with guselkumab treatment or response to treatment (from select sites). Cells isolated from the urine sample will be cryopreserved and may later be examined by single cell transcriptomics to identify signatures associating with LN or SLE pathogenesis and signatures associating with guselkumab treatment or response to treatment.

8.8.4. Stopping Analysis

Biomarker analyses are dependent upon the availability of appropriate biomarker assays and clinical response rates. Biomarker analysis may be deferred or not performed, if during or at the end of the study, it becomes clear that the analysis will not have sufficient scientific value for biomarker evaluation, or if there are not enough samples or responders to allow for adequate biomarker evaluation. In the event the study is terminated early or shows poor clinical efficacy, completion of biomarker assessments is based on justification and intended utility of the data.

8.9. Immunogenicity Assessments

Antibodies to guselkumab will be evaluated in serum samples collected from all participants according to the SoA. Additionally, serum samples should also be collected at the final visit from participants who discontinued study intervention or were withdrawn from the study. These samples will be tested by the sponsor or sponsor's designee.

Serum samples will be screened for antibodies binding to guselkumab and the titer of confirmed positive samples will be reported. Other analyses may be performed to verify the stability of antibodies to guselkumab and/or further characterize the immunogenicity of guselkumab.

Serum samples will be used to evaluate the immunogenicity of anti-guselkumab antibodies. Samples collected for immunogenicity analyses may additionally be used to evaluate safety or efficacy aspects that address concerns arising during or after the study period. Genetic analyses will not be performed on these serum samples. Participant confidentiality will be maintained.

Analytical Procedures

The detection and characterization of antibodies to guselkumab will be performed using a validated assay method by or under the supervision of the sponsor. All samples collected for detection of antibodies to guselkumab will also be evaluated for guselkumab serum concentration to enable interpretation of the antibody data. Antibodies may be further characterized and/or evaluated for

their ability to neutralize the activity of the study intervention(s). Samples may be stored up to 15 years (or according to local regulations) following the last participant's last visit for the study at a facility selected by the sponsor to enable further analysis of immune responses to guselkumab.

8.10. Medical Resource Utilization and Health Economics

Not applicable.

9. STATISTICAL CONSIDERATIONS

Due to the sponsor's decision to terminate the study early, some analyses described below may not be performed. The primary efficacy analysis and most secondary efficacy analyses will be performed. All safety analyses will be performed.

For informational purposes, the below section outlines the original statistical plan.

Statistical analysis will be done by the sponsor or under the authority of the sponsor. A general description of the statistical methods to be used to analyze the efficacy and safety data is outlined below.

Specific details will be provided in the revised SAP.

9.1. Statistical Hypotheses

The primary hypothesis of this study is that guselkumab plus standard-of-care is superior to placebo plus standard-of-care in participants with active LN as measured by the proportion of participants inducing at least a 50% reduction of proteinuria with protocol specified steroid tapering regimen at Week 24.

9.2. Sample Size Determination

The original design of the study included a target of approximately 60 participants to be randomly assigned, with approximately 30 participants planned per intervention group. Due to the sponsor's decision to stop screening of new participants as a result of enrollment challenges, fewer than 60 participants will be enrolled in the study.

It should be noted that the sample size determination below was calculated assuming approximately 60 participants would be randomized in this study.

The study will be considered a success if the 1-sided p-value from the difference in proportion of participants with $\geq 50\%$ decrease in proteinuria between the guselkumab and placebo intervention groups from a logistic mixed effect repeat measurement (MMRM) longitudinal model is less than a 1-sided alpha of 10%.

[Table 7](#) shows the sensitivity of power to detect a difference in proportions of participants with $\geq 50\%$ decrease in proteinuria between the guselkumab and placebo intervention groups at Week 24.

Table 7: Power to Detect Difference in Proportions of Participants with $\geq 50\%$ Decrease in Proteinuria Between the Guselkumab and Placebo Intervention Groups at Week 24

Difference in proportion of participants with $\geq 50\%$ decrease in proteinuria between the intervention groups	Power (%)
20%	56.34
25%	79.61
30%	89.84
35%	96.08

Notes:

- Proportion of placebo participants with $\geq 50\%$ decrease in proteinuria is assumed to be 49%.
- Power calculation is based on 1-sided α of 0.10.
- Total sample size is 60.

If the proportion of placebo participants with $\geq 50\%$ decrease in proteinuria is 49%, and the difference in proportion between the intervention groups is 30%, a total sample size of 60 with a 1-sided alpha of 10% will provide approximately 90% power for success.

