Difference in proportion of participants with $\geq 50\%$ decrease in proteinuria between the intervention groups	Power (%)
20%	56.34
25%	79.61
30%	89.84
35%	96.08

Notes:

- Proportion of placebo participants with $\geq 50\%$ decrease in proteinuria is assumed to be 49%.
- Power calculation is based on 1-sided α of 0.10.
- Total sample size is 60.

If the proportion of placebo participants with $\geq 50\%$ decrease in proteinuria is 49%, and the difference in proportion between the intervention groups is 30%, a total sample size of 60 with a 1-sided alpha of 10% will provide approximately 90% power for success.

Primary Endpoint Analysis

Analyses of the primary efficacy endpoint ($\geq 50\%$ decrease in proteinuria from baseline at Week 24) will include data from all randomized participants who received at least one administration of study intervention based on their assigned intervention group, regardless of the actual intervention received and have baseline data (Evaluable population).

Treatment Failure Criteria may include: initiation or increased use of a glucocorticoid or other immunosuppressive agents, however these will be further defined in the SAP.

Participants who meet any of the TF criteria defined in the SAP will be assumed a non-responder, ie, did not meet the $\geq 50\%$ decrease in proteinuria criteria at Week 24.

The primary analysis will be based on the composite estimand where participants meeting TF criteria are assumed non-achievers from the point of TF forward, and missing data are assumed as non-achievers as well.

The study will be considered a success if the 1-sided p-value from the difference in proportion of participants with $\geq 50\%$ decrease in proteinuria between the guselkumab and placebo intervention groups from a logistic MMRM longitudinal model is less than a 1-sided alpha of 10%.

See the SAP for further details about the analysis of the primary endpoint, including sensitivity and subgroup analyses.

Major Secondary Analyses

The major secondary endpoints are listed above. The Evaluable population will be used for analysis and participants will be counted in the intervention group assigned, regardless of the study intervention received.

Treatment failure and missing data will be included in the secondary endpoint estimands as non-achievers or non-responders.

The details of the analysis of the major secondary endpoints will be included in the SAP.

Safety Analyses

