An external, independent Data Monitoring Committee (DMC) will be commissioned for this study. The DMC will review unblinded data on a periodic basis to ensure the safety of participants enrolled in the study. The main focus of the DMC will be on reviewing interim unblinded safety data, but the DMC may also review efficacy data needed to ensure the full benefit:risk profile for guselkumab. The DMC responsibilities, authorities, and procedures will be documented in a separate DMC charter.

NUMBER OF PARTICIPANTS

A target of approximately 60 participants will be randomly assigned in a 1:1 ratio to study intervention in this study, with approximately 30 participants planned per intervention group.

INTERVENTION GROUPS AND DURATION

Participants in the study will maintain their standard-of-care treatment of mycophenolate mofetil (MMF)/mycophenolic acid (MPA) and background glucocorticoid. Participants' glucocorticoid dose will be tapered.

Participants will be randomized to 1 of 2 intervention groups in a 1:1 ratio as described below:

- Guselkumab: Participants will receive guselkumab 400 mg intravenously (IV) at Weeks 0, 4 and 8 (ie, 3 IV doses) and guselkumab 200 mg subcutaneous (SC) every 4 weeks (q4w) from Week 12 through Week 48.
- Placebo: Participants will receive placebo IV at Weeks 0, 4 and 8 (ie, 3 IV doses) and placebo SC q4w from Week 12 through Week 48.

Participants will be stratified by geographic region (North America, Latin America, Asia Pacific and Europe) and Urine Protein to Creatinine Ratio (UPCR) level (<3 mg/mg and ≥ 3 mg/mg).

[figure not shown]
Participants will remain on their assigned treatment through Week 48. All participants will receive an IV infusion (either active or placebo) at Weeks 0, 4, and 8 and 2 SC injections (either active or placebo) at Week 12 then q4w through Week 48.

Eligible participants will continue to receive the same study intervention q4w (placebo or guselkumab) in the LTE. The first dose in the LTE will be at Week 52.

The study participants will remain blinded throughout the study (including the LTE). Due to study termination, one DBL for the study will occur at the end of study. The end of study will occur after all enrolled participants have completed the Week 20 visit or discontinued study intervention prior to Week 24, and all participants have completed their final efficacy and safety visits per the SoA.

The study schema is provided in [Figure 1](#).

Figure 1: Schematic Overview of the Study

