3. SAMPLE SIZE DETERMINATION

Early Termination Note: Due to the Sponsor's decision to stop screening of new participants as a result of enrollment challenges, fewer than 60 participants will be enrolled in the study. The end of study will occur after all enrolled participants have completed the Week 20 visit or discontinued study intervention prior to Week 24, and all participants have completed their final efficacy and safety visits per the SoA.

The sample size section below is the originally planned sample size.

Approximately 60 participants are planned to be randomized into the study.

The study will be considered a success if the 1-sided p-value for testing the difference in proportion of participants with $\geq 50\%$ decrease in proteinuria between the guselkumab and placebo

intervention groups based on a logistic mixed effect repeat measurement longitudinal model is less than a 1-sided alpha level of 10%.

Table 1 shows the sensitivity, with respect to various assumed between group difference, of estimated power to detect a difference in proportions of participants with $\geq 50\%$ decrease in proteinuria between the guselkumab and placebo intervention groups at Week 24.

Table 1: Power to Detect Difference in Proportions of Participants with $\geq 50\%$ Decrease in Proteinuria Between the Guselkumab and Placebo Intervention Groups at Week 24

Difference in proportion of participants with $\geq 50\%$ decrease in proteinuria between the intervention groups	Power (%)
20%	56.34
25%	79.61
30%	89.84
35%	96.08

Notes:

- Proportion of placebo participants with $\geq 50\%$ decrease in proteinuria is assumed to be 49%.
- Power calculation is based on 1-sided α of 0.10.
- Total sample size is 60.

If the proportion of placebo participants with $\geq 50\%$ decrease in proteinuria is 49%, and the difference in proportion between the intervention groups is 30%, a total sample size of 60 with a 1-sided alpha of 10% will provide approximately 90% power for success.

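### The 20-point row of the power table (56.34%) does not fit the table's sample size of 60; the calculation that reproduces the other three rows gives 65.87%

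*Protocol*

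**What the plan says.** Protocol Section 9.2 (Table 7), the protocol Synopsis and SAP Section 3 (Table 1) print the same four powers:

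| Difference (points) | Printed power (%) |
|---|---|
| 20 | 56.34 |
| 25 | 79.61 |
| 30 | 89.84 |
| 35 | 96.08 |

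The notes under each table apply to every row: a placebo response rate of 49%, "Power calculation is based on 1-sided α of 0.10", and "Total sample size is 60". Protocol Section 9.2 adds: "It should be noted that the sample size determination below was calculated assuming approximately 60 participants would be randomized in this study". SAP Section 1.2 gives the allocation: "A target of approximately 60 participants will be randomly assigned in a 1:1 ratio to study intervention in this study", about 30 per group. No row is marked as using a different sample size.

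The success criterion in both documents is a 1-sided p-value below 0.10 from a logistic longitudinal mixed model. Neither document says which test or software produced the powers. After the decision to terminate early, both keep the section as a record of the original plan.

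**The concern.** The printed powers rise by 23.27 points from the first row to the second (79.61 − 56.34), then by 10.23 (89.84 − 79.61) and 6.24 (96.08 − 89.84). The first step looks too large for a single calculation at one sample size, which suggests that the first row was not produced in the same way as the others.

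If so, a stated power contradicts the sample-size note beneath it, in three places across two documents. A reader who uses the table to judge the original design would take the chance of success at a 20-point effect to be little better than even. The figure could also be carried into later reporting.

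**Working it through.** **Inputs.** Placebo rate 0.49, 1-sided alpha 0.10 and total N = 60 come from the table notes. The 1:1 allocation comes from SAP Section 1.2, so n = 30 per arm. Guselkumab rates are 0.49 plus the difference: 0.69, 0.74, 0.79 and 0.84. The sample-size section states no dropout inflation, so none is applied.

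**Formula.** Let X be the number of responders on placebo, Y the number on guselkumab, and p̄ = (X + Y)/(2n). The unadjusted z statistic is

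z = (Y/n − X/n) / √[ p̄(1 − p̄)(2/n) ],

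rejecting when z > 1.2816. Exact power is the sum, over all pairs (x, y) that reject, of

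Bin(x; n, 0.49) × Bin(y; n, 0.49 + difference).

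The unpooled standard error gives the same powers at 25 and at 30 per arm.

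**Results (%).**

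| Difference (points) | Printed | n = 30 per arm (N = 60) | n = 25 per arm (N = 50) |
|---|---|---|---|
| 20 | 56.34 | **65.873** | **56.338** |
| 25 | 79.61 | 79.611 | 70.682 |
| 30 | 89.84 | 89.841 | 83.090 |
| 35 | 96.08 | 96.083 | 92.232 |

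The plan's own figures are reproduced at N = 60 for 25, 30 and 35 points. The 20-point row is not: 65.87 − 56.34 = 9.53 points. The printed value is the N = 50 result. With 65.87 in the first row, the step to the second becomes 79.61 − 65.87 = 13.74, in line with the later steps of 10.23 and 6.24.

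**How specific the match is.** Among all pairs of arm sizes from 15 to 40, equal or unequal, only 25 and 25 give 56.34 at 20 points. Among equal arm sizes in that range, only 30 gives the printed value in each of the other three rows.

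**Other methods at N = 60, 20-point row (%).**

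| Method | Power |
|---|---|
| Normal approximation, pooled null variance | 61.78 |
| Same, 2-sided | 47.15 |
| Normal approximation, unpooled | 62.82 |
| Normal approximation, fully pooled | 61.54 |
| Arcsine | 62.00 |
| Log odds ratio | 61.05 |
| Continuity-corrected normal | 51.26 |
| Exact power, Mantel-Haenszel variance | 64.36 |
| Exact power, Fisher's test | 55.65 |

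Fisher's test comes closest to 56.34, but it gives 71.10, 83.97 and 92.89 for the other rows. No single method tried at N = 60 reproduces all four. The pooled normal approximation at 25 per arm also gives 56.34, so either approach points to N = 50 for that row.

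**The case against.** The strongest objection concerns weight. Both documents keep this text as the original plan, fewer than 60 participants will be enrolled, and no analysis, success criterion or stopping rule uses the 20-point row. Only the 30-point row is used to justify 60 participants, and it reproduces. All of this stands and limits the consequence.

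The second objection is that no test is named, so the size of the gap depends on an inferred method. The pooled normal approximation would put it at 5.4 points (61.78 − 56.34), and Fisher's test would put it at −0.7 (55.65 − 56.34). That is correct as arithmetic, but neither method reproduces the other three rows, whereas the unadjusted z test matches all three to two decimals. A simulated or covariate-adjusted mixed model would be very unlikely to match them three times and then miss once by 9.5 points. The N = 50 origin remains an inference; neither document mentions 50 participants or 25 per arm.

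The third objection is that the inferred test does not hold its nominal level. With both rates at 0.49, its actual 1-sided type I error is 12.25% at 30 per arm and 10.13% at 25 per arm. So 65.87% is power at a nominal 0.10 cutoff that the test exceeds. This is a fair caveat, but it applies equally to the three matching rows and does not rescue 56.34.

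**Conclusion.** The concern holds. Under the only method found that reproduces the 25-, 30- and 35-point rows, the 20-point row at N = 60 should read 65.87%, not 56.34%, a difference of 9.5 points. The printed figure was most likely computed at N = 50. This rests on two inferences, an unadjusted two-proportion z test as the method and 25 per arm as the source of the odd row, and the sponsor's output can settle both.

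The consequence is limited. The error understates power, it sits in a sensitivity row, and it leaves the 30-point row (89.84%, described as approximately 90%) and the choice of 60 participants unaffected.

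**What to change.** The sponsor should check the program output behind the table. If it confirms the above, replace 56.34 by 65.87 in the Synopsis table, Protocol Table 7 and SAP Table 1.

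Once the method is confirmed, add one note under each table saying that the powers are for an unadjusted two-proportion test at a nominal 1-sided alpha of 0.10, not for the planned logistic mixed model. The note could also record that the actual level at 30 per arm is about 12% when both rates are 49%.

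The cost is one number and one note in three tables across two documents. Neither the trial nor its analyses change.
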